Furthermore, it would not be possible to compare the two treatments (everolimus, sunitinib) to each other and to other treatments from a statistical perspective. This is because the population size needed for a statistically significant comparison based on, for example, the criterion of mortality, would take over 6 years of recruitment to reach (if 4 treatment groups were compared, with the hypothesis of a 20% relative reduction in mortality, and 250 patients needed per group, so 1000 patients²) given that the target population is estimated at 150 patients per year. Furthermore, it was important to consider that at the same time there are a number studies in France recruiting from the same limited population (at least four studies known of) which would have an even greater effect on the feasibility and potential for inclusion.

These issues and the similarity of the two study requests made by HAS led the two pharmaceutical companies to consider a single observational study, estimating the impact on morbidity and mortality at 2 years of well-differentiated, unresectable or metastatic, progressive pancreatic neuroendocrine tumours (pNET) in adults.

In order to answer the questions from HAS, two broad groups of treatments were decided upon:

- The "targeted therapies" group, made up of two sub-groups:
 - Everolimus (AFINITOR®)
 - Sunitinib (SUTENT®)
- The "other treatments" group, made up of four sub-groups of the most commonly prescribed treatments:
 - Chemotherapy
 - Somatostatin analogues
 - Interferon alpha
 - Radionuclide therapy

Local treatments (chemoembolization, radiofrequency ablation etc.) and surgery were excluded in order to ensure sufficient population numbers to meet the objectives.

-

² Case set out in detail as sent by Novartis to HAS in a letter of 7th March 2012

3. Objectives of the study

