3.2. Secondary objectives

This study will also enable us to meet the following secondary objectives:

- To describe the characteristics of the population of adult patients treated for a welldifferentiated, unresectable or metastatic, progressive pancreatic neuroendocrine tumour
- To describe the management of patients with well-differentiated, unresectable or metastatic, progressive pancreatic neuroendocrine tumours and treated with targeted therapies and other treatments (types of treatment, treatment regimens and prescription modalities)

This is a national observational, descriptive, prospective (partially retrospective), multicentre study carried out in France in adult patients treated for a well-differentiated, unresectable or metastatic, progressive pancreatic neuroendocrine tumour.

The study will be carried out in sites involved in the management of neuroendocrine tumours of the pancreas.

These sites will be identified from a database of doctors specialised in oncology, gastroenterology and endocrinology built up as part of this study by the two sponsors. Patients who meet the eligibility criteria will be invited to enrol in the study until the required number is met, and each patient may only be enrolled once in the study. The patient's therapeutic management will not be altered by taking part in the study and it will follow the recommendations made in a Multidisciplinary Team Meeting (MDTM) in accordance with good practice guidelines.

The inclusion phase is 28 months and will enable us to prospectively include patients seen for a consultation or hospital admission during the inclusion phase and treated by targeted therapies (Everolimus or Sunitinib) or by another treatment (one of those defined as part of this study: chemotherapy somatostatin analogues, radionuclide therapy or interferon alpha), for which the following apply:

- Treatment is started as first, second, third or fourth line treatment at the time of enrolment in the study with a change of treatment line being defined as a change of drug or combination thereof (incident cases)
- The treatment ongoing at inclusion was started as a first, second, third or fourth line therapy prior to enrolment in the study as long as treatment was started at the same site that is enrolling the patient in the study (prevalent cases)

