4.7. Derived Variables

• Total duration of exposure to the documented treatment in the study (months)

(Date of last receipt of treatment – Date of first receipt of treatment + 1)/30.4375

For patients who drop out of the study early, the date of last receipt of the treatment considered will be the date of the last visit.

To analyse exposure times by treatment received at least once during the study, if the start date is after the date of the last visit, the treatment will not be considered.

In terms of exposure time for treatments used in combination, the start date and end date of the combination were not recorded in the CRF. The visit prior to the report describing addition of the combination will be deemed to be the start date and the visit in which the combination is reported as being discontinued will be deemed to be the end date for the combination, unless the combination began or finished during a line of treatment (or includes the start and end date).

• In general, the time between two dates expressed in days will be obtained as follows:

Most recent date – Least recent date

The following conversion factors will be used to convert the times into months or years:

- 1 month = 30.4375 days
- 1 year = 365.25 days
- Age (in years) will be calculated as follows:

(Inclusion date – Date of birth)/365.25

• The disease duration (in years) will be calculated as follows:

(Inclusion date – Disease start date)/365.25

• The disease duration (in years) at start of the current treatment at inclusion will be calculated as follows:

(Treatment start date - Diagnosis date) / 365.25

• Time until first temporary discontinuation since inclusion into the study:

(Date of first temporary discontinuation – Date of inclusion + 1)/30.4375

• Time until permanent treatment discontinuation since inclusion into the study:

(Date of final discontinuation – Date of inclusion + 1)/30.4375

• Lines of cancer treatment:

Treatment lines will be defined in two ways:

- Main treatment line: All new treatments will be considered as a new main treatment line.
- Main concomitant treatment line: All new treatments or new combinations will be deemed to be a new concomitant treatment line.

The reason for discontinuing treatment will not be considered in the definition of a treatment line.

The same treatment stopped for over 3 months will be deemed to be two different lines of treatment and to be one line if the discontinuation lasts for less than 3 months.

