The treatment lines will be counted differently depending on whether they are a previous treatment or a treatment administered during the study and whether the date of collection is retrospective or prospective.

Prior treatment lines only include systemic treatments (chemo-embolisation will not be deemed to be a previous treatment line) whereas treatment lines during the study will be deemed to be as such whether they are systemic or locoregional treatments (chemo-embolisation will be deemed to be a treatment line in this case).

Treatment with Lutathera will be considered to be metabolic radiotherapy.

If the combination involves a somatostatin analog (as the main treatment), then the combination becomes the main treatment unless surgery is involved. The start date of the main treatment is the date of the visit recording the combination (and this same date will be considered as the discontinuation date of the previous line). The discontinuation of the main treatment also corresponds to the date when the treatment was discontinued before starting a new line.

Moreover, if Pazopanib is recorded as the previous "other" treatment it should then be reclassified as targeted therapy and presented as the 3rd targeted therapy line (in addition to Everolimus and Sunitinib).

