5.9.3. Therapeutic Pathway of Patient

The therapeutic pathway of the patient will be described based on the three treatments (main treatment line: Targeted therapy, Chemotherapy and Somatostatin analogs).

Targeted therapy

The targeted therapy will be described for each period (overall follow-up, before inclusion, after inclusion) and as follows:

- Number of patients having received at least one targeted therapy.
- Number of patients having received Everolimus at least once.
- Number of patients having received Sunitinib at least once.
- Number of patients having received Pazopanib at least once.
- Number of patients having received Everolimus at least once and Sunitinib at least once.
- Number of patients having received Everolimus at least once, but not Sunitinib or Pazopanib.
- Number of patients having received Sunitinib at least once, but not Everolimus or Pazopanib.
- Number of patients who never received targeted therapy.
- Number of targeted therapies received per patient (quantitative and by class: 0 / 1 / 2 / 3 / 4 and more).

Targeted therapy will be described for the entire follow-up based on:

• Number of patients having received two different targeted therapies (Everolimus and Sunitinib, or Everolimus and Pazopanib).

In addition, the position of the targeted therapy in the care pathway of the patient will be described for the entire follow-up:

- Number of patients having received a targeted therapy as the 1st, 2nd, 3rd, nth main treatment line.
- Number of patients having received a targeted therapy immediately before/after chemotherapy.
- Number of patients having received a targeted therapy immediately before/after a somatostatin analog (as main treatment).

The duration of the targeted therapy (in months) and reasons for the discontinuation will also be described irrespective of the targeted therapy and by differentiating between Everolimus and Sunitinib during the period before inclusion then after inclusion.

The total duration of the targeted therapy (obtained by adding the periods before inclusion and after inclusion) will be described.

The analysis and duration of the targeted therapy (irrespective of the targeted therapy) and the reasons for the discontinuation will also be presented based on the following subgroups:

- Main treatment lines during follow-up (1/2/.../n).
- Number of patients with ≤ 2 lines, ≥ 2 main treatment lines for the entire follow-up.
- Ki67 (the most recent prior to inclusion) ($\leq 10\% / > 10\%$).

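### Locoregional treatment counts as a line only after inclusion, so whole-pathway line numbers depend on when the patient was included

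*SAP*

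**What the plan says.** The protocol's design text defines a line by its drugs, "with a change of treatment line being defined as a change of drug or combination thereof". SAP 3.3 carries the same definition in its eligibility text.

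SAP 4.7 adds a working rule for analysis. A main line is opened by each new treatment: "All new treatments will be considered as a new main treatment line". The count then depends on the period: "The treatment lines will be counted differently depending on whether they are a previous treatment or a treatment administered during the study". Before inclusion only systemic treatments count: "chemo-embolisation will not be deemed to be a previous treatment line) whereas treatment lines during the study" count "whether they are systemic or locoregional treatments (chemo-embolisation will be deemed to be a treatment line in this case".

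The two counts are put on one scale. SAP 5.9.6 describes main lines across the retrospective and prospective phases together, and the footnote to Table 14.2.2.2.10 forms the total by adding prior lines to on-study lines. SAP 5.9.3 uses that scale for the position of targeted therapy, for example "Number of patients having received a targeted therapy as the 1st, 2nd, 3rd, nth main treatment line". SAP 5.9.5, 5.9.7 and 5.9.8 use it to form subgroups.

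**The concern.** A line number should describe a patient's treatment history. Here it also depends on where in that history the patient was included. Two patients with identical treatment sequences can carry different numbers for the same drug and fall on opposite sides of a subgroup cut.

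Describing how patients are managed, including the types of treatment used, is a stated secondary objective. The line number also defines groups for toxicity discontinuation, progression-free survival and overall survival. Those tables would compare groups formed by two counting rules. Neither the SAP's list of amendments (5.8) nor its limitations (Section 6) mentions this, and no sensitivity analysis under a common rule is planned.

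**Working it through.** The plan states no figure for this rule, so the check applies the rule to fixed pathways and moves only the inclusion point.

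**Rule.** The line number of a treatment is the number of counted treatments up to and including it. Under SAP 4.7 a systemic treatment always counts 1. A locoregional treatment counts 0 before inclusion and 1 after it. Inclusion is always on a systemic treatment, as eligibility requires.

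**Results under the SAP rule** (SSA = somatostatin analogue, CE = chemo-embolisation opening its own main line, EVE = everolimus, CT = chemotherapy):

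| Pathway | Included on | EVE line | Total lines | First targeted therapy | Total group |
|---|---|---|---|---|---|
| SSA, CE, EVE | SSA | 1+1+1 = 3 | 3 | 3 or more | >2 |
| SSA, CE, EVE | EVE | 1+0+1 = 2 | 2 | 1 or 2 | ≤2 |
| SSA, CE, EVE, CT | SSA | 3 | 4 | 3 or more | >2 |
| SSA, CE, EVE, CT | EVE or CT | 2 | 3 | 1 or 2 | >2 |
| SSA, CT, CE, EVE | SSA or CT | 1+1+1+1 = 4 | 4 | 3 or more | >2 |
| SSA, CT, CE, EVE | EVE | 1+1+0+1 = 3 | 3 | 3 or more | >2 |

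The first pathway changes group on both cuts, the second on one, and the third on neither although its numbers shift.

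**Controls.** SSA, EVE, CT has no locoregional step: EVE is line 2 and the total is 3 at every inclusion point. In CE, SSA, EVE the procedure precedes any possible inclusion: EVE is line 2 and the total is 2 at either point. The period-dependent rule is therefore the cause.

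**One rule for both periods.** For SSA, CE, EVE, systemic-only counting makes everolimus line 2 at either inclusion point. Counting locoregional treatment throughout makes it line 3 at either. Both remove the dependence on inclusion.

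**Reach in the SAP.**
- 5.9.3: position of targeted therapy, and its duration by line and by total lines.
- 5.9.5: toxicity discontinuation by total lines, and by second-line treatment.
- 5.9.6: main lines over both periods.
- 5.9.7: progression-free survival by second-line treatment, by line of first targeted therapy, by total lines in chemotherapy patients, and for post-inclusion lines.
- 5.9.8: overall survival by first targeted therapy in line 1 or 2 against 3 or more, and for post-inclusion lines.

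Unaffected: subgroups by line at inclusion, which use prior systemic counts only; the number of lines during the study, which follows one rule; and the overall analysis of overall survival.

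**The case against.** The rule is deliberate, openly stated, and follows how the data were collected. Before inclusion the CRF has a separate locoregional section and a separate table of systemic lines; the SAP template (Table 14.1.4.1.8) shows the former as yes/no by type. During the study one table takes all cancer treatment lines, including free-text others. This stands as an explanation. It shows why prior procedures cannot be placed in sequence, but not why on-study ones should then be numbered on the same scale.

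The affected results are mainly additional analyses. Table 14.2.2.3.1 splits sequences by period and Listing 16.2.5 has a period column, so a careful reader could see where the rule changes. That is also true, but the subgroup tables themselves show no such split.

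Four stronger readings are tempting and are not supported:
- *Patients included earlier have longer follow-up in which to gain lines.* Planned prospective follow-up is 24 months from inclusion for everyone.
- *Every patient with an on-study procedure moves group.* Under SAP 4.7 a procedure recorded as a combination with a main treatment other than an analogue opens a concomitant line, not necessarily a main line. A shift in position also needs a later treatment. The position of a first targeted therapy received at or before inclusion is already fixed. Assuming that 10 to 20% have a procedure gives 15 to 30 of 150, but the documents do not supply that share, and it would not be the number crossing a given cut.
- *The primary progression-free survival result is biased by the line number.* That analysis follows the main treatment at inclusion and is not grouped by line number. When that treatment ends can depend on a separate SAP 4.7 rule about combinations with an analogue, which is a different question.
- *The protocol forbids counting local treatment as a line.* Protocol Section 2 says "Local treatments (chemoembolization, radiofrequency ablation etc.) and surgery were excluded in order to ensure sufficient population numbers to meet the objectives". That sets the study treatment groups and does not say how later treatments are numbered. SAP Appendix 1 also lists chemo-embolisation among chemotherapy protocols, so whether it changes the drug combination is arguable.

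**Conclusion.** The point holds for line numbers, totals and positions that span both periods. Following the SAP as written, patients with the same treatment sequence can be placed in different line groups because of their inclusion date alone. This is a comparability flaw in secondary and additional descriptive analyses.

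The size per patient is one line for each on-study locoregional treatment that opens a main line. It crosses the ≤2 / >2 cut only when the systemic total is 2 or less and the added lines take it above 2. It crosses the 1–2 / 3-or-more cut only when the first targeted therapy is the second systemic line and the procedure falls between inclusion on the first line and the start of that therapy. The number of patients concerned cannot be computed, because the documents give neither the frequency nor the timing of on-study procedures. The conclusion rests on reading SAP 4.7 literally and on at least some pathways having a locoregional step between possible inclusion points.

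**What to change.** In SAP 4.7, state that for every line number, total or position spanning both periods, only systemic treatments are counted, before and during the study. Apply this to 5.9.3 and 5.9.5 to 5.9.8 and their tables. State that chemo-embolisation, although listed in Appendix 1, is not counted as a chemotherapy line in these analyses. Report on-study locoregional treatments in a separate table built like Table 14.1.4.1.8. Systemic-only is the workable common rule, since prior procedures cannot be placed in order from the data shown.

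Leave unchanged the rule for when the inclusion treatment ends in the primary progression-free survival analysis; altering it would change which events count there. The new numbering should therefore be a separate derived variable.

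The cost is SAP wording, one derived variable and one table, with no new data. The small downside is that local procedures no longer appear inside the numbered sequence.

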5. STATISTICAL ANALYSES

In all of the analyses, somatostatin analogs (octreotide, lanreotide) will be grouped into one single group, except for the description of treatment at inclusion.

5.1. Dates of the Study

The following data will be described globally:

- inclusion date of the first patient,
- inclusion date of the last patient,
- duration of inclusions (months),
- date of last visit of last patient,
- duration of the study (between first inclusion and last visit).

5.2. Distribution of Doctors

The numbers and percentages of active and inactive doctors will be described.

5.3. Distribution of Patients

A summary table will show the numbers and percentages of patients (prevalent and incident patients and total number of patients) in each population in each group and globally:

- Number of non-included patients;
- Number of included patients;
- Number and percentage of patients in the safety analysis set;
- Number and percentage of patients in the reference set.

Percentages will be calculated from the population of included patients.

The following parameters will also be described:

- Reasons for non-inclusion in the reference set;
- Centre characteristics: number of centres, number of patients per centre;
- Reasons for dropping out of the study in the safety analysis set and reference set;
- Patient status at the end of the study (alive/dead/lost to follow-up) in the safety analysis set and reference set;
- Protocol deviations.

Patients excluded from the reference and safety analysis sets with their reasons for non-inclusion will be listed.

5.4. Baseline Characteristics

5.4.1. Description of Patients

Descriptive statistics will be used for the demographic data and baseline patient characteristics analysis. These parameters will be presented globally and by analysis group in the reference set and will also be described in each of the two patient subgroups treated with targeted therapy at inclusion:

- everolimus (AFINITOR®),
- sunitinib (SUTENT®).

and in the 4 subgroups of patients treated with another treatment at inclusion:

- chemotherapy,
- somatostatin analogs,
- interferon alpha,
- metabolic radiotherapy.

The demographic characteristics will include patient age and sex at inclusion into the study. They will be presented in the population of included patients and in the reference set.

The following parameters will also be described at inclusion in the reference set:

- ECOG Index.
- Past medical history and concomitant diseases (the LVEF value (%) will be presented as classes <50% vs ≥50%).
- Proportion of patients with a past history of at least one comorbidity (all comorbidities listed plus "OTHERS" category).
- Proportion of patients with a past history of at least one comorbidity of interest (only the set of comorbidities listed).
- Number of treated comorbidities of interest in the past history by patient (quantitative analysis and by classes 0, 1-3, >3).
- Proportion of patients with a past history of at least one treated comorbidity of interest (only the set of comorbidities listed).
- Number of treated comorbidities of interest per patient in the patient's past history (quantitative analysis and analysis by classes 0, 1-3, >3).
- History of the disorder: duration, type of tumour at diagnosis, previous locoregional cancer treatments, surgery, investigations performed.
- Previous lines of cancer treatments: number of lines, type of treatments and combinations, duration, reasons for discontinuation.
- Current treatment: type and details of cancer treatment, presentation of the list of chemotherapies defined according to the main treatment protocols (see Appendix 1), time between starting treatment and inclusion, time between diagnosis and starting treatment (overall analysis and by group depending on the position of the treatment line, whether ongoing or administered at inclusion), temporary discontinuations, antisecretory agent treatments, presence of metastases.

5.4.2. Description of Doctors

The participating doctors will be described using the following parameters: specialty, type of practice, type of facility, active file.

5.4.3. Representativeness of Samples of Doctors and Patients

Comparisons will be made between active doctors who took part in the study (who included at least one patient) and inactive doctors who did not include any patients, by calculating standardised differences.

These standardised differences will be calculated as follows:

Type of variable	Equation			
Qualitative	$d = \frac{P_1 - P_2}{\sqrt{\frac{P_1(1 - P_1) + P_2(1 - P_2)}{2}}}$			
	P ₁ : proportion of individuals with the feature in group 1			
	P ₂ : proportion of individuals with the feature in group 2			
Quantitative	$d = \frac{\text{moy}_1 - \text{moy}_2}{\sqrt{\frac{\text{var}_1 + \text{var}_2}{2}}}$			
	mean ₁ : mean in group 1			
	mean ₂ : mean in group 2			
	var ₁ : variance in group 1			
	var ₂ : variance in group 2			

Similarly, comparisons will be made between included and non-included patients based on information collected in the non-inclusion register (age, sex), The reasons for non-inclusion will be presented. The "others" reasons for non-inclusion will be listed.

In addition, patients who are lost to follow-up and/or dropped out of the study (for a reason other than death) will be compared to patients with complete follow-up (follow-up until progression, death, end of main treatment ongoing at the time of inclusion or 2-year cutoff date) in the reference set.

We will deem the observed difference to be small if the standardised difference is between [0.2 and 0.3], average if between [0.3-0.8] and large if it is over 0.8. A value of 0.2 or less will be considered to represent no difference.

